3.6 Discontinuation of Investigational Product

Patients may be discontinued from IP in the following situations:

- Patient decision; the patient is at any time free to discontinue treatment, without prejudice to further treatment
- AE
- Severe noncompliance with the Clinical Study Protocol
- Pregnancy
- Patient incorrectly initiated on study treatment
- Objective disease progression and patient is no longer receiving clinical benefit
- Lost to follow-up
- Patient starts receiving additional anticancer therapy

Patients experiencing any of the following AEs will not be permitted to restart study treatment:

- ILD/pneumonitis
- QTc interval prolongation with signs/symptoms of serious arrhythmia (see [Table 4](#))
- Grade 3 or higher adverse reaction that does not improve to Grade 0 to 2 after withholding study treatment for up to 3 weeks

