6.8 Management of Investigational Product-Related Toxicities

Dose adjustment for AEs should be in accordance with the following table:

Table 4 Osimertinib Dose Adjustment Information for Adverse Reactions

Target organ	Adverse reaction	Dose modification
Pulmonary	Interstitial lung disease/pneumonitis	Permanently discontinue osimertinib
Cardiac	QTc interval greater than 500 msec on at least 2 separate ECGs	Withhold osimertinib until QTc interval is less than 481 msec or recovery to baseline if baseline QTc is more than 481 msec within 3 weeks of interruption, then restart at a reduced dose (40 mg) or at 80 mg (at the discretion of the Investigator, to allow for situations where causality in relation to osimertinib may be difficult to determine)
	QTc interval prolongation with signs/symptoms of serious arrhythmia	Permanently discontinue osimertinib
Cutaneous	Stevens-Johnson Syndrome and toxic epidermal necrolysis (TEN)	Permanently discontinue osimertinib
Blood and lymphatic system	Aplastic anaemia	Permanently discontinue osimertinib
Other	Grade 3 or higher adverse reaction	Withhold osimertinib for up to 3 weeks
	If Grade 3 or higher adverse reaction improves to Grade 0-2 after withholding of osimertinib for up to 3 weeks	Osimertinib may be restarted at the same dose (80 mg) or a lower dose (40 mg)
	Grade 3 or higher adverse reaction that does not improve to Grade 0-2 after withholding for up to 3 weeks	Permanently discontinue osimertinib

Note: The intensity of clinical adverse events graded by the NCI CTCAE version 4.0.
ECG = electrocardiogram; CTCAE = Common Terminology Criteria for Adverse Event; NCI = National Cancer Institute; QTc = QT interval corrected for heart rate; TEN = toxic epidermal necrolysis.

If a patient experiences a CTCAE Grade 3 or higher adverse reaction, and/or unacceptable toxicity, including a dose-limiting toxicity (DLT), not attributable to the disease or disease-related processes under investigation, dosing will be interrupted, and supportive therapy administered as required in accordance with local practice/guidelines.

If a toxicity resolves or reverts to \leq CTCAE Grade 2 within 3 weeks of withholding osimertinib, treatment with osimertinib may be restarted at the same dose or a lower dose

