6.8.4 Erythema multiforme, Stevens-Johnson syndrome and toxic epidermal necrolysis

Case reports of EM and TEN have been uncommonly reported, and SJS have been rarely reported, in association with osimertinib treatment. Before initiating treatment, patients should be advised of signs and symptoms of EM, SJS and TEN. If signs and symptoms suggestive of EM develop, close patient monitoring and drug interruption or discontinuation of osimertinib should be considered. If signs and symptoms suggestive of SJS appear, osimertinib should be interrupted. Osimertinib should be discontinued immediately if diagnosis of SJS or TEN is confirmed.

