6.8.5 Aplastic anaemia

Rare reports of aplastic anaemia have been reported in association with osimertinib treatment. Some cases had a fatal outcome. Before initiating treatment, patients should be advised of signs and symptoms of aplastic anaemia including but not limited to persistent fever, bruising, bleeding, pallor. If signs and symptoms suggestive of aplastic anaemia develop, close patient monitoring and drug interruption or discontinuation of osimertinib should be considered. Osimertinib should be discontinued in patients with confirmed aplastic anaemia.

Permanent discontinuation due to toxicity

Patients experiencing ILD, QTc prolongation with signs/symptoms of serious arrhythmia or Grade 3 or higher adverse reaction that does not improve to Grade 0 to 2 after withholding for up to 3 weeks will not be permitted to restart study treatment.

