7.2 Dose and Treatment Regimens

Osimertinib is administered as 80 mg once daily. Osimertinib can be taken without regard to food.

Doses should be taken approximately 24 hours apart at the same time point each day. Doses should not be missed. If a patient misses taking a scheduled dose, within a window of 12 hours, it is acceptable to take the dose. If it is more than 12 hours after the dose time, the missed dose should not be taken, and patients should be instructed to take the next dose at the next scheduled time. If a patient vomits after taking their osimertinib, they should not make up for this dose, but should take the next scheduled dose.

The dose of 80 mg osimertinib daily can be reduced to 40 mg osimertinib once daily under circumstances described in Section 6.8. Further dose reductions are not possible. Once a dose has been reduced, it should not be re-escalated at future cycles.

Any change from dosing schedule, dose interruptions or dose reductions should be recorded.

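### Both no-restart lists omit SJS, TEN and aplastic anaemia, which Table 4 marks for permanent discontinuation, and the QTc restart text does not fit the re-escalation rule for patients already at 40 mg

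*Protocol*

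**What the plan says.** **Events after which treatment is not resumed.** The protocol states these in several places.

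- Section 3.6 opens its list with "Patients experiencing any of the following AEs will not be permitted to restart study treatment". Three items follow: ILD/pneumonitis; QTc prolongation with signs or symptoms of serious arrhythmia; and a Grade 3 or higher reaction that has not come down to Grade 0 to 2 after up to 3 weeks of withholding.
- The paragraph headed Permanent discontinuation due to toxicity, at the end of section 6.8.5, gives the same three: "Patients experiencing ILD, QTc prolongation with signs/symptoms of serious arrhythmia or Grade 3 or higher adverse reaction that does not improve" within the same 3 weeks.
- Table 4 in section 6.8 assigns permanent discontinuation to those three and to two more rows: "Stevens-Johnson Syndrome and toxic epidermal necrolysis (TEN") under the cutaneous heading, and "Aplastic anaemia" under blood and lymphatic system.
- Section 6.8.4 adds: "Osimertinib should be discontinued immediately if diagnosis of SJS or TEN is confirmed". Section 6.8.5 adds: "Osimertinib should be discontinued in patients with confirmed aplastic anaemia".

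**Dose on restart.** After a QTc interval above 500 msec, the QTc row of Table 4 and section 6.8.2 both give two options, 40 mg or 80 mg, the second at the Investigator's discretion. Neither mentions the dose the patient was taking before the interruption. Section 7.2 says: "Once a dose has been reduced, it should not be re-escalated at future cycles".

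The SAP sets no restart or dose rule, so it does not settle either point.

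**The concern.** A stopping rule stated in more than one place should have the same content in each. Section 3.6 is the protocol's general section on discontinuing the investigational product, so it is a natural place for a site to check whether a patient may resume. Its list does not say that it is a selection, and it refers to Table 4 only in the QTc item. The closing paragraph of section 6.8.5 directly follows the aplastic anaemia instruction, yet leaves that event out.

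The reactions concerned are serious; section 6.8.5 notes that some aplastic anaemia cases were fatal. On the dose side, an Investigator treating a patient at 40 mg after a QTc event can find protocol text that leaves 80 mg open and other text that advises against it.

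There is also a smaller data consequence. Treatment discontinuation is an event in time to treatment discontinuation or death (protocol 8.4.2, SAP 3.2.2.5), and dose reductions and interruptions are summarised (SAP 4.2.8). Both record what sites did, and unclear rules make that less uniform.

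**Working it through.** No figure in the plan bears on this point, so the check compares the texts.

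**Part 1: the lists against Table 4**

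| Permanent-discontinuation row in Table 4 | List in 3.6 | Closing list in 6.8.5 | Own section |
|---|---|---|---|
| ILD/pneumonitis | yes | yes | 6.8.1 |
| QTc prolongation with serious arrhythmia | yes | yes | – |
| SJS and TEN | **no** | **no** | 6.8.4: discontinue once confirmed |
| Aplastic anaemia | **no** | **no** | 6.8.5: discontinue once confirmed |
| Grade 3 or higher, not improved to Grade 0–2 in up to 3 weeks | yes | yes | – |

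Table 4 has 5 rows and each list covers 3, so 5 − 3 = 2 rows are missing. They are the same two rows in both lists.

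The gap can be bounded further. A case of SJS, TEN or aplastic anaemia of Grade 3 or higher that does not improve within 3 weeks is caught by the last item of both lists. The lists are silent on a case that does improve to Grade 0–2 in that time. Table 4 makes no exception for improvement in these rows.

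**Part 2: restart after QTc above 500 msec, by dose before the interruption**

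- *Patient on 80 mg.* The QTc row and section 6.8.2 allow 40 mg or 80 mg. Withholding is an interruption, not a reduction, so resuming 80 mg is not re-escalation. Section 7.2 is not engaged and there is no conflict.
- *Patient already reduced to 40 mg.* The QTc row and section 6.8.2 allow the same two options, because they set no condition on prior dose. Section 7.2 applies, because a reduction has taken place, and says the dose should not go back up. The passages disagree on whether 80 mg is open to this patient.

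The collision is therefore confined to patients at the reduced dose who then have a QTc event of this kind.

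**The case against.** **No passage permits restart after SJS, TEN or aplastic anaemia.** This is correct. Section 6.8 says dose adjustment should follow Table 4, and Table 4, 6.8.4 and 6.8.5 all call for discontinuation. The list in 3.6 does not claim to be exhaustive, and the same section names an adverse event as a ground for discontinuation. A site that restarted after one of these reactions would be departing from Table 4. The point is therefore an omission, not two opposed instructions. It still stands, because someone using either list alone would not see these events.

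**A reader might infer that the row of Table 4 for other Grade 3 or higher reactions opens restart after an SJS or aplastic anaemia case that improves.** The table does not support that. The row is the residual category, and these reactions have rows of their own.

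**A reader might also infer that this row conflicts with section 7.2.** It says "Osimertinib may be restarted at the same dose (80 mg) or a lower dose (40 mg"). By equating the same dose with 80 mg, it describes a patient who was on 80 mg. For someone on 40 mg, 80 mg is neither the same nor lower, so the row gives no permission to increase. The text under Table 5 on later interruptions mentions no increase either.

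**The QTc row might likewise have been written with a patient on 80 mg in mind,** since it calls 40 mg a reduced dose. That is a plausible account of the drafting. But the row does not describe 80 mg as the same dose. The reason it gives for discretion, uncertain causality, could apply equally to a patient at 40 mg. The literal wording still meets section 7.2 head on.

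**Conclusion.** The point holds in two limited parts.

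1. The no-restart lists in 3.6 and at the end of 6.8.5 are each incomplete against Table 4, by the same two of five rows. This is inconsistency by omission.
2. For a patient already at 40 mg who has a QTc above 500 msec, the QTc row of Table 4 and section 6.8.2 leave open a dose that section 7.2 advises against.

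Few patients are expected to be affected. Section 6.8.4 describes SJS as rarely reported and TEN as uncommonly reported, and section 6.8.5 speaks of rare reports of aplastic anaemia. The second part needs both a prior reduction and a later QTc event. The documents do not give the frequencies needed to calculate either number.

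A reader might scale the 10% dose-reduction rate that section 1.1 reports for 80 mg in an earlier first-line cohort. That would estimate patients who ever had a reduction, not those who then had a qualifying QTc event, and the 80 mg group had only 30 patients. It does not measure the size of this problem.

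The case for correcting the text rests on the gravity of the reactions and the low cost of the change, not on an expected effect on the study's estimates.

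**What to change.** - Reconcile section 3.6, the closing paragraph of section 6.8.5, Table 4, section 6.8.4 and the aplastic anaemia text of section 6.8.5, so that one consistent list of no-restart events applies wherever the rule is stated.
- Reconcile the QTc row of Table 4, section 6.8.2 and section 7.2, so that they say the same thing about restart for a patient already at the reduced dose.

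The sponsor's safety physician decides which rule stands in each case; this review takes no view on that.

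The cost is wording in a few protocol sections, with no new procedure and no effect on sample size or analysis. Section 9.3 plans for the study to end by Q2 2023, so the practical need is for patients still on treatment. Appendix A 5 names protocol amendments and letters to Investigators as ways to address safety issues, and a letter would be enough to reach those sites.

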3.6.1 Procedures for discontinuation of a patient from investigational product

At any time, patients are free to discontinue IP or withdraw from the study (ie, IP and assessments; see [Section 3.7](#)) without prejudice to further treatment. A patient that decides to discontinue IP will always be asked about the reason(s) and the presence of any AEs. If possible, they will be seen and assessed by an Investigator(s). AEs will be followed up (see [Section 6](#)); all study drugs should be returned by the patient.

Study procedures related to serious adverse events (SAEs) and anticancer treatment must be captured until the patient no longer has RECIST 1.1 assessments (disease progression or permanent withdrawal from the study).

If a patient is withdrawn from the study, see [Section 3.7](#).

3.7 Criteria for Withdrawal

3.7.1 Screen failures

Screening failures are patients who do not fulfil the eligibility criteria for the study, and therefore must not be treated in the study.

These patients should have the reason for study withdrawal recorded as 'Screen failure' (ie, the potential patient who does not meet one or more criteria required for participation in a trial). For those patients, only demography data and reason for discontinuation will be recorded. Supporting safety information can be collected in case of a SAE, if applicable.

Patients who initially fail screening due to out of range laboratory values will be allowed to repeat the laboratory assessment within the Screening Period, and if the repeat laboratory values are compliant with the inclusion/exclusion criteria, the patient may be enrolled into the study and receive study treatment. For patients who experience a temporary acute medical event that would prohibit enrolment of the patient within the normal duration of the Screening Period, discussion of an extension of the Screening Period with the medical monitor may occur. Otherwise, patients will not be rescreened and the patient identification number for screen failures will not be re-used.

3.7.2 Withdrawal of informed consent

Patients are free to withdraw from the study at any time (IP and assessments) without prejudice to further treatment. Withdrawal of consent should be clearly documented in the patient notes and in the eCRF.

A patient who withdraws consent will always be asked about the reason(s) and the presence of any AEs. The Investigator will follow-up AEs outside of the clinical study.

If a patient withdraws from participation in the study, then his/her enrolment code cannot be re-used. Withdrawn patients will not be replaced.

3.8 Discontinuation of the Study

The study may be stopped if, in the judgement of AstraZeneca, trial patients are placed at undue risk because of clinically significant findings that:

- Meet individual stopping criteria or are otherwise considered significant
- Are assessed as causally related to study drug
- Are not considered to be consistent with continuation of the study

Regardless of the reason for termination, all data available for the patient at the time of discontinuation of follow-up must be recorded in the eCRF. All reasons for discontinuation of treatment must be documented.

4 STUDY PLAN AND TIMING OF PROCEDURES

The Schedule of Assessments for the screening visit is shown in [Table 1](#). On study assessments are shown in [Table 2](#).

4.1 Screening/Enrolment Period

At screening, consenting patients are assessed to ensure that they meet eligibility criteria. Patients who do not meet these criteria must not be enrolled in the study.

Procedures will be performed according to [Table 1](#) within 28 days prior to Day 1.

The following assessments need to be repeated for patients where > 28 days will have lapsed since their last Screening Period to the date of proposed enrolment.

Table 1 Screening (Visit 1) Study Schedule

Day	Day -28 to -1
Informed consent	X

Day	Day -28 to -1
Assignment of unique enrolment number (IVRS/IWRS)	X
Demography and baseline characteristics	X
Medical and surgical history	X
Inclusion/exclusion criteria	X
Physical examination including weight and eyes	X
WHO performance status (0-1)	X
Vital signs (includes blood pressure, pulse and temperature), height	X
Haematology/clinical chemistry	X
ECG	X
Echocardiogram/MUGA ^d	X
Prior cancer therapies including radiotherapy	X
Urinalysis	X
Pregnancy test ^a	X
Tumour assessment (CT or MRI according to RECIST 1.1) ^b	X
AEs (from time of consent)	X
Concomitant medications	X
Tumour tissue ^c	X
Plasma sample for ctDNA and blood-borne biomarkers	X

^a WoCBP must have a negative urine or serum pregnancy test within 28 days prior to starting treatment and a confirmatory test before treatment on Day 1. In the event of suspected pregnancy during the study, the test should be repeated and, if positive, the patient discontinued from study treatment immediately. Monthly pregnancy testing and monitoring of WoCBP is recommended, however this schedule may be modified to comply with local legislation.

^b RECIST assessments will be performed using CT or MRI scans of the chest, abdomen and pelvis and should be performed no more than 28 days before the first treatment, and as close as possible to the start of study treatment.

^c For central collection and baseline resistance profiling; testing will be conducted at a later date. The first mandatory tumour tissue biopsy may be an archival or fresh tissue sample obtained within 60 days of study entry. An archival biopsy is acceptable as long as no intervening anticancer treatment occurred since the time the biopsy was obtained to enrolment in this study, and as long as it is within 60 days of study entry.

^d To be performed at least every 16 weeks throughout the treatment period up to 3.5 years and then at least every 20 weeks for the remainder of the treatment period. The modality of the cardiac function assessments must be consistent within a patient, ie, if echocardiogram is used for the screening assessment, then echocardiogram should also be used for subsequent scans.

AE = adverse event; CT = computed tomography; ctDNA = circulating tumour deoxyribonucleic acid; ECG = electrocardiogram; IVRS/IWRS = interactive voice response system/interactive web response system; MRI = magnetic resonance imaging; MUGA = multigated acquisition scan; RECIST = Response Evaluation Criteria in Solid Tumours; WHO = World Health Organization; WoCBP = women of childbearing potential.

Table 2 Study Schedule – On Study Treatment and Discontinuation

	Screening/ Enrolment ^a	Treatment Period (further treatment cycles as per C7) ^b								Treatment discontinued	Follow-up Period	28 days ^c	Progression follow-up ^d
		1	2	3	4	5	6	7, 8, 9	10+				
Visit Number	Cycles / Day	C1			C2	C3	C4, 5, 6	C7 to 3.5 years	3.5 Years to Disease Progression	D1278+			
		D1	D 8	D15	D1	D1	D1	D169-1277	D1278+				
Day	-28 to -1	1	8	15	29	57	85, 113, 141	Every 8 weeks	Every 10 weeks				Every 8 weeks prior to Day 1277/ Every 10 weeks thereafter
Window (Days)		0	± 2	± 2	± 2	± 7	± 7	± 7	± 14		± 7	+ 7	± 7/± 14
Informed consent	x												
IVRS/IWRS	x												
Demography and baseline characteristics	x												
Medical/surgical history	x												
Inclusion/exclusion criteria	x	x											
Pregnancy test (WOCBP) ^e	x	x											
Tumour tissue sample ^d	x ^d												
Tumour tissue sample on treatment (optional) ^e				x ^e									
Tumour tissue sample upon disease progression ^f										x ^f			
Plasma sample for ctDNA and blood-borne biomarkers	x	x pre-dose	x	x	x	x	x	x	x	x ^{b, g}			

	Screening/ Enrolment ^a	Treatment Period (further treatment cycles as per C7) ^b								Treatment discontinued	28 days ^c	Progression follow-up ^d
		1	2	3	4	5	6	7, 8, 9	10+			
Visit Number	1											
Cycles / Day		C1			C2	C3	C4, 5, 6		C7 to 3.5 years	3.5 Years to Disease Progression		
		D1	D 8	D15	D1	D1	D1		D169-1277	D1278+		
Day	-28 to -1	1	8	15	29	57	85, 113, 141		Every 8 weeks	Every 10 weeks		Every 8 weeks prior to Day 1277/ Every 10 weeks thereafter
Window (Days)		0	± 2	± 2	± 2	± 7	± 7		± 7	± 14	± 7	+ 7
Whole blood sample at progression ^e											x	
Physical examination, including weight and eyes ^h	x	x			x	x	x		x	x	x	
Height	x											
WHO performance status	x	x			x	x	x		x	x	x	once at start of subsequent anticancer treatment
Vital signs	x	x	x	x	x	x	x		x	x	x	
Clinical chemistry/ Haematology/ Urinalysis ^h	x	x	x	x	x	x	x		x	x	x	
ECG ⁱ	x	x	x	x	x	x	x		x	x	x	
Echocardiogram/ MUGA (for LVEF) ^j	(x)	At least every 16 weeks up to 3.5 years on study drug and then at least every 20 weeks for as long as on study drug								If clinically indicated		

	Screening/ Enrolment ^a	Treatment Period (further treatment cycles as per C7) ^b								Treatment discontinued	28 days ^c	Progression follow-up ^d
		1	2	3	4	5	6	7, 8, 9	10+			
Visit Number	1											
Cycles / Day		C1			C2	C3	C4, 5, 6		C7 to 3.5 years	3.5 Years to Disease Progression		
		D1	D 8	D15	D1	D1	D1		D169-1277	D1278+		
Day	-28 to -1	1	8	15	29	57	85, 113, 141		Every 8 weeks	Every 10 weeks		Every 8 weeks prior to Day 1277/ Every 10 weeks thereafter
Window (Days)		0	± 2	± 2	± 2	± 7	± 7		± 7	± 14	± 7	+ 7 ± 14
Tumour assessments (RECIST) ^k	x				x	C5D1 and every 8 weeks until Day 1277			Every 10 weeks until progression			x
Dispense study medication	x				x	x	x	x	x			
Dose with osimertinib							Daily dosing					
Concomitant medication and procedures	x	x	x	x	x	x	x	x	x	x	x	(once) ^l
AEs	x	x	x	x	x	x	x	x	x	x	x	(once) ^l
First subsequent anticancer therapy ^m											x	x

^a Consent must be taken prior to 28-day Screening Period. The Screening Period will start with first study-related assessment.

^b Six 4-week cycles followed by 8-week cycles from Cycle 7 to 3.5 years (Day 1277), and 10-week cycles from 3.5 years to disease progression. Patients who continue to receive osimertinib beyond RECIST 1.1-defined progression, if continuing to show clinical benefit to treatment as judged by the Investigator, will continue to follow the treatment visit schedule and assessments excluding study specific RECIST assessments and plasma samples for ctDNA and blood-borne biomarkers.

^c As a minimum, telephone contact should be made with the patient 28 days (window + 7 days) following the discontinuation of study drug (last dose of IP).

- d For baseline resistance profiling; testing will be conducted at a later date. The first mandatory tumour tissue biopsy may be an archival or fresh tissue sample obtained within 60 days of study entry. An archival biopsy is acceptable as long as no intervening anticancer treatment occurred since the time the biopsy was obtained to enrolment in this study, and as long as it is within 60 days of study entry.
- e The optional on-treatment biopsy may be performed between Day 15 and Day 21 of Cycle 1.
- f The second mandatory tumour tissue biopsy may be performed any time between Investigator-assessed, RECIST 1.1-defined progression and before the start of any new anticancer treatment. If a patient discontinues osimertinib before RECIST 1.1-defined progression, the second biopsy will not be performed.
- g Plasma samples for ctDNA and blood-borne biomarkers will only be obtained at the treatment discontinuation visit.
- h If screening assessments have been performed within 14 days prior to starting study treatment, they do not have to be repeated on Visit 2 if the patient's condition has not changed. The assessments are to be completed pre-dose on visit day. Laboratory tests may be performed the day prior to study visits.
- i ECG is also to be performed in event of any cardiac AE.
- j To be performed at least every 16 weeks throughout the treatment period up to 3.5 years and then at least every 20 weeks for the remainder of the treatment period. The modality of the cardiac function assessments must be consistent within a patient, ie, if echocardiogram is used for the screening assessment, then echocardiogram should also be used for subsequent scans. The patients should also be examined using the same machine and operator whenever possible, and quantitative measurements should be taken. A 28-day follow-up assessment will be required if an on-treatment assessment was abnormal at the time of discontinuation of study therapy, to confirm reversibility of the abnormality.
- k The screening assessment should be performed within 28 days prior to study drug initiation. Subsequent assessments are to be performed every 8 weeks (\pm 7 days) from study enrolment until 3.5 years (Day 1277), and then every 10 weeks (\pm 14 days) until RECIST 1.1-defined progression, even if a patient discontinues treatment prior to progression or receives other anticancer treatment. Tumour assessment will be performed using CT or MRI of the chest, abdomen (including liver and adrenal glands) and pelvis. Any other sites where disease is suspected or known at screening must also be imaged.
- l If the first scheduled progression follow-up visit falls before the 28-day follow-up visit, then AEs and concomitant medications will be assessed at this visit in addition to the 28-day follow-up visit.
- m In addition to tumour assessments, patients will be followed for the earlier of first subsequent anticancer therapy (including surgical) after discontinuing osimertinib or death.
- n At progression, a whole blood sample will be obtained within 7 days of when the tissue biopsy is performed.
- o The progression biopsy should be done prior to the start of subsequent anticancer treatment.
- p Monthly pregnancy testing and monitoring of WOCBP is recommended, however this schedule may be modified to comply with local legislation.

AE = adverse event; C = cycle; CT = computed tomography; ctDNA = circulating tumour deoxyribonucleic acid; D = day; ECG = electrocardiogram; IVRS/IWRS = interactive voice response system/interactive web response system; LVEF = left ventricular ejection fraction; MRI = magnetic resonance imaging; MUGA = multigated acquisition scan; RECIST = Response Evaluation Criteria in Solid Tumours; WHO = World Health Organization; WOCBP = women of childbearing potential.

